The two most recent measurements of serum testosterone prior to Day 1 of protocol therapy must fulfill the following criteria:

- Both measurements are greater than 150 ng/dL.
- The two measurements are spaced at least 14 days apart.
- Both must be measured within 3 months of Day 1 of protocol therapy.
- There must not be an increase of > 50 ng/dL between these two successive measurements.
- 10. PSA doubling time (PSADT) ≤ 15 months, calculated based upon all serum PSA measurements obtained within 3 months prior to Day 1 of protocol therapy, witha minimum of three PSA measurements spaced at least 14 days apart (see section 6). PSA values obtained when serum testosterone was known to be less than 150 ng/dL, prior to local therapy, or within three months of last dose of LHRH agonist/antagonist or antiandrogen will be excluded from the calculation of the PSADT.PSADT calculation to be carried out using the following website:

http://nomograms.mskcc.org/Prostate/PsaDoublingTime.aspx

- 11. Total bilirubin less than 1.5 times upper limit of normal (ULN), or less than 3 times ULN at study entry in a patient with documented Gilbert"s disease.
- 12. ALT and AST levels less than 1.5 times ULN at study entry
- 13. Serum potassium greater than 3.5 mmol/L without oral supplementation
- 14. No history of uncontrolled hypertension (blood pressure > 160/100 mm Hg despite antihypertensive medication)
- 15. ECOG performance status of 0 or 1
- 16. Estimated life expectancy greater than 5 years
- 17. Age greater than or equal to 18 years at time of study entry
- 18. Ability to sign written informed consent

Phase II - Itraconazole

- 19. Ability to swallow study drug whole as a capsule
- 20. Primary prostate cancer tissue available for analysis is not required for inclusion onto this study but is strongly encouraged.
- 21. Patients who have partners of childbearing potential must be willing to use a method of birth control with adequate barrier protection as determined to be acceptable by the principal investigator and sponsor during the study and for 1 week after last study drug administration.

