6.3.5 Laboratory/Radiographic Assessment

The frequency and schedule of laboratory and radiographic assessment is outlined above in the study schedule. Serum PSA will be measured on a monthly basis while patients are receiving protocol therapy. A whole body bone scan (either Na-F PET or technetium-99 bone scan), along with cross-sectional imaging of the abdomen/pelvis (CT or MRI) will be obtained at baseline and at the time of PSA or clinical progression, whichever occurs first.

Liver function tests and serum sodium and potassium levels will be measured pre-study, on day 8 +/- 3 days, day 28 +/- 7 days, then every 4 weeks +/- 7 days thereafter. BUN/serum creatinine will be measured pre-study and every 4 weeks +/- 7 days.

Serum itraconazole and hydroxy-itraconazole levels will be measured at the day 28 (+/- 7 days) study visit. Hormone levels (outlined above in the study schedule) will be measured at baseline, day 28 (+/- 7 days), and week 12 (+/- 7 days) of protocol therapy.

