8.0 Dosage Modifications/Toxicity

8.1 Toxicity

Toxicities and Adverse Events will be assessed during each monthly clinic visit using the NCI CTCAEversion 4.03. Since CTEP has standardized the CTC, the NCI does not require the inclusion of the CTCAE within this protocol document. However, all appropriate treatment areas will have access to a copy of the CTCAEversion 4.03. A copy can be downloaded from the CTEP home page: http://ctep.cancer.gov

Dose re-escalation after prior dose reduction due to toxicity will not be permitted.

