8.2.2 Management of Elevated Liver Function Tests

If Grade 1 increases in AST, ALT, or total bilirubin occur (AST or ALT > ULN – 3.0 x ULN or bilirubin > ULN – 1.5 x ULN), the frequency of LFT monitoring will be increased to bi-weekly but dose reduction and/or delay will not be mandated. If Grade 2 increases in AST, ALT or total bilirubin occur (AST or ALT > $3.0 - 5.0 \times$ ULN or bilirubin > $1.5 - 3.0 \times$ ULN, itraconazole will be held until the LFT abnormality improves to Grade 1 or lower, at which point the study drug will be restarted at 400 mg/day. If a grade 2 increase in AST, ALT, or bilirubin recurs, itraconazole will be held until improved to Grade 1 or lower in severity, and then restarted at 200 mg/day. If Grade 3 increases in AST, ALT, or bilirubin occur (AST or ALT > $5.0 - 20.0 \times$ ULN or bilirubin > $3.0 - 10.0 \times$ ULN, itraconazole will be held until the LFT abnormality improves to Grade 1 or lower (AST or ALT > $5.0 - 20.0 \times$ ULN or bilirubin > $3.0 - 10.0 \times$ ULN, itraconazole will be held until the LFT abnormality improves to Grade 1 or lower, at which point study drug may be restarted at 200 mg/day per individual investigator discretion. If a grade 3 increase in AST, ALT, or bilirubin recurs, itraconazole will be permanently discontinued. If a grade 4 increase in AST, ALT, or bilirubin occurs, itraconazole will be permanently discontinued. Any treatment delay greater than 4 weeks will result in permanent discontinuation of itraconazole.

AST or ALT	Grade of LFT		Further
Bilirubin	Abnormality	Action	Action/Maintenance
>ULN - 3X ULN > ULN - 1.5 X ULN	1	Increase frequency of LFT monitoring to bi-weekly	None
> 3.0 – 5.0 X ULN > 1.5 – 3.0 X ULN	2	Hold itraconazole; increase frequency of LFT monitoring to weekly	If improves to Grade 1 or lower, re-initiate at 400 mg/day. If recurrent grade 2 AE, hold until Grade 1 or lower, then re-start at 200 mg/day.
> 5.0 – 20.0 X ULN > 3.0 – 10.0 X ULN	3	Hold itraconazole; increase frequency of LFT monitoring to weekly	If improves to Grade 1 or lower, re-initiate at 200 mg/day per investigator discretion. If recurrent grade 3 AE, perman- ently discontinue itraconazole.
> 20.0 X ULN > 10.0 X ULN	4	Permanently discontinue itraconazole	N/A

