8.3 Dose Modification for Other Adverse Events

For adverse events of grade 1 in severity, treatment will be per institutional guidelines, and no dose interruption will be mandated. For adverse events of grade 2 in severity that the study investigator deems as possibly, probably or definitely related to study drug, treatment will be interrupted until the adverse event resolves to grade ≤ 1 in severity, at which point itraconazole will be re-started at a reduced dose of 400 mg/day. If a patient experiences a recurrent adverse event of grade 2 in severity, itraconazole will be held until the adverse event resolves to grade ≤ 1 in severity, at which point itraconazole will be held until the adverse event resolves to grade ≤ 1 in severity, at which point itraconazole will be held until the adverse event resolves to grade ≤ 1 in severity, at which point itraconazole will be re-started at 200 mg/day.

Treatment will be interrupted for grade 3 adverse events that study investigator attributed as possibly, probably, or definitely related to study medication. Treatment will be held until the adverse event resolves to grade ≤ 1 in severity, at which point therapy will be re-instituted at a reduced dose of 200 mg/day. If the adverse event recurs to grade 2 in severity, treatment will be held until the adverse event resolves to grade ≤ 1 in severity, at which point therapy will be re-instituted at 200 mg/day per individual investigator discretion. If the adverse event recurs to grade 3 or higher in severity, treatment will be permanently discontinued and patients will not be re-challenged for any grade 4 adverse events occurring while receiving protocol therapy.

Grade of Other AE	Action	Further Action/Maintenance
1	Treatment per institutional guidelinesNo dose interruption will be mandated	None
2	 Treatment interrupted until the adverse event resolves to grade ≤ 1 in severity @ ≤ 1 in severity, re-start itraconazole at reduced dose of 400 mg/day 	 If recurrent grade 2 AE, hold itraconazole until resolves to grade ≤ 1 in severity @ ≤ 1 in severity, re-start itraconazole at reduced dose of 400 mg/day

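### Minor: inclusion criterion 11 admits men with Gilbert's disease at bilirubin below 3 x ULN, but section 8.2.2 lets drug restart after a bilirubin hold only at 1.5 x ULN or lower

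*Combined protocol and SAP*

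**What the plan says.** **Entry (4.2, item 11).** Total bilirubin must be below 1.5 x ULN, "or less than 3 times ULN at study entry in a patient with documented" Gilbert's disease. This is the only place where the documents mention Gilbert's disease.

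**Dose modification (8.2.2).** Bilirubin is graded in fixed multiples of ULN:
- Grade 1: above ULN to 1.5
- Grade 2: above 1.5 to 3.0
- Grade 3: above 3.0 to 10.0
- Grade 4: above 10.0

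"If Grade 2 increases in AST, ALT or total bilirubin occur", drug is "held until the LFT abnormality improves to Grade 1 or lower, at which point the study drug will be restarted at 400 mg/day". After a Grade 3 hold the same level of Grade 1 or lower applies, "at which point study drug may be restarted at 200 mg/day per individual investigator discretion". The section adds: "Any treatment delay greater than 4 weeks will result in permanent discontinuation of itraconazole". Section 8.1 adds: "Dose re-escalation after prior dose reduction due to toxicity will not be permitted".

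**Monitoring (6.3.5).** "Liver function tests and serum sodium and potassium levels will be measured pre-study, on day 8 +/- 3 days", then at day 28 and every 4 weeks.

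**Primary analysis (10.8.1).** A man with at least one follow-up PSA who stops protocol therapy before 12 weeks, whatever the reason, is a failure.

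**The concern.** The eligibility criteria make an allowance for Gilbert's disease that the dose rules do not carry forward. The clause matters only for entry values from 1.5 to just under 3 x ULN, because anyone below 1.5 is eligible without it. Apart from exactly 1.5, all of those values lie above the level at which 8.2.2 allows drug to restart.

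Once such a man is held for bilirubin, going back to his own normal is not enough. He must fall below the value at which the protocol accepted him, within 4 weeks, or lose study drug for good. He would then count against itraconazole in the primary analysis for a reason unrelated to PSA response. If he does fall far enough after a Grade 2 hold, he continues at 400 mg/day, which is 400/600 = two thirds of the dose named in the primary objective, with no way back up.

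**Working it through.** **1. Thresholds side by side (total bilirubin, x ULN)**

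| Rule | Range |
|---|---|
| Eligible without Gilbert's disease (4.2, item 11) | < 1.5 |
| Eligible only through the Gilbert clause | 1.5 to < 3 |
| Grade 2, hold (8.2.2) | > 1.5 to 3.0 |
| Grade 3, hold (8.2.2) | > 3.0 to 10.0 |
| Restart level after either hold (8.2.2) | ≤ 1.5 |

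For other patients the two sections fit: entry bilirubin below 1.5 x ULN is at most Grade 1, and so is entry AST or ALT below 1.5 x ULN (Grade 1 runs to 3.0). Only the Gilbert band fails to fit.

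**2. The restart level, which does not depend on how the trigger is read**
- Entry 2.0, rise to 2.8, return to 2.0: held at Grade 2; back at his entry value, but 2.0 > 1.5, so no restart.
- Entry 2.9, drift to 3.1, return to 2.9: held at Grade 3; 2.9 > 1.5, so no restart.

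**3. The hold trigger, on the literal reading only**
- An unchanged 2.0 lies in the Grade 2 band at the first on-treatment test, Day 8 ± 3 = Day 5 to 11.
- The 4-week limit passes at Day 5 + 28 = Day 33 to Day 11 + 28 = Day 39.
- Week 12 is Day 84, so he would be stopped 84 − 39 = 45 to 84 − 33 = 51 days (about 6 to 7 weeks) before it.

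More generally, a hold that begins before Day 84 − 28 = Day 56 and is never released becomes a permanent stop before week 12.

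**4. Scale**

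Inputs from 10.2: 22 men in stage 1, continue if more than 2 respond, 40 in total, reject at 8 or more, null 10%, alternative 25%.

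P(reject) = Σ over x = 3 to n₁ of P[Bin(n₁, p) = x] × P[Bin(n₂, p) ≥ 8 − x]

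With n₁ = 22 and n₂ = 18 this gives power 0.803 at 25%, type I error 0.040 at 10%, and probability 0.620 of stopping at stage 1 under the null. The plan's figures (80%, 0.05, 0.62) reproduce.

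Now assume one man in 40 is a forced failure. This is hypothetical; the documents give no count. He can be removed from those able to respond in stage 1 (n₁ = 21) or in stage 2 (n₂ = 17):

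| | None | One, stage 1 | One, stage 2 |
|---|---|---|---|
| Power at 25% | 0.803 | 0.776 | 0.782 |
| Type I error at 10% | 0.040 | 0.034 | 0.035 |
| P(≤ 2 responders in stage 1) at 25% | 0.061 | 0.075 | 0.061 |

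The loss of power is 2.7 points (stage 1) or 2.1 points (stage 2). With no such man, or one who restarts and responds as expected, it is nil.

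**The case against.** The strongest defence is that 8.2.2 is triggered by increases that occur, and a man steady at 2 x ULN has had none. Section 6.3.2 allows interruptions for toxicity, Section 8 is headed as a toxicity section, and 6.3.4 takes a Day 1 adverse event assessment as baseline. A known, unchanged Gilbert bilirubin is hard to call a toxicity, and item 11 admits these men on purpose. This has force. A reader might infer that every man admitted through the clause must be held at Day 8 and lost. The documents do not support that as a certainty, because the trigger can be read either way.

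The defence does not reach the restart level, which is a fixed multiple of ULN with no reference to entry. Attribution offers no escape: the condition "that the study investigator deems as possibly, probably or definitely related to study drug" stands in 8.3, for other adverse events, and 8.2.2 has no equivalent. The general re-challenge sentence in 11.3 does not say that it overrides the specific 4-week stop.

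It is also fair to say that a strict liver rule is defensible for a drug with liver failure among its rare serious risks (7.1), and that harm needs several conditions at once: documented Gilbert's disease, entry above 1.5 x ULN, a hold, and bilirubin staying above 1.5 x ULN for more than 4 weeks. The documents give no frequency for any of them. That limits the point to minor; it does not remove it.

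**Conclusion.** The point holds as a minor one. It is certain that 8.2.2 sets a restart level that a man enrolled above 1.5 x ULN cannot meet by returning to his entry value, and that the 4-week stop and the failure rule in 10.8.1 then follow if this happens before week 12 and he has a follow-up PSA. Whether an unchanged entry value triggers the Grade 2 hold at Day 8 is unclear from the text.

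The number of men affected is not stated and may be zero. The 2 to 3 points of power per forced failure are an illustration, so it would be wrong to infer that the trial is underpowered: the design figures are correct as stated. Any effect is conservative. It can lower the observed response proportion, and it does not inflate type I error.

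**What to change.** Add one sentence to the text of 8.2.2, and mirror it in the table. For patients enrolled under the Gilbert clause of item 11:
- the Grade 2 bilirubin hold (above 1.5 to 3.0 x ULN) does not apply;
- bilirubin holds start above 3.0 x ULN, the ceiling that item 11 already accepts;
- the condition for restart is return to the study-entry bilirubin or lower.

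The AST and ALT rules, the Grade 4 stop, the reduced restart doses and the 4-week limit stay as they are. A man who enters at 2.9 and drifts to 3.1 x ULN would still be held, and at the investigator's discretion could restart at 200 mg/day; what changes is that he can restart once back at 2.9.

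The cost is one sentence, with no extra visits, tests or patients. The downside is a slightly less cautious bilirubin rule in these few men, with AST and ALT monitoring unchanged. Deleting the Gilbert clause would also remove the mismatch, but it gives up a deliberate eligibility allowance to settle something that a sentence can settle.

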4.3 Exclusion Criteria

- 1. Castrate-resistant disease, as evidenced by either:
 - Rising PSA on 2 consecutive measurements at least 2 weeks apart with concurrent documented serum testosterone < 50 ng/dL at the time of PSA measurement, or
 - Rising PSA on 2 consecutive measurements at least 2 weeks apart measured within 3 months after last LHRH agonist/antagonist injection
- 1. Prior bilateral orchiectomy
- 2. Congestive heart failure of NYHA class III or higher severity at study entry
- 3. History of chronic active hepatitis
- 4. Grade 2 or higher peripheral neuropathy at the time of study entry
- 5. Use of 5-alpha reductase antagonist (i.e. finasteride, dutasteride) or antiandrogen (i.e. flutamide, bicalutamide) within 6 weeks of Day 1 of protocol therapy
- 6. Use of systemic steroids at an equivalent dose of prednisone 5 mg/day or higher within 6 weeks of Day 1 of protocol therapy
- 7. Use of medications or herbal supplements which are known to potentially lower serum PSA within 6 weeks of Day 1 of protocol therapy (see appendix 1 for list of medications)
- 8. Use of other medications that may potentially interact with itraconazole within 1 week of study entry (see appendix 2 for list of medications)
- 9. Use of other investigational agents within 6 weeks of Day 1 of protocol therapy
- 10. Prior pathology consistent with small cell carcinoma or prostate cancer with predominantly neuroendocrine differentiation

5.0 Study Rationale

5.1 Rationale for the Study Population

Patients with biochemically relapsed, non-castrate, non-metastatic prostate adenocarcinoma after prior definitive local therapy will be enrolled onto this study. Both patients without prior ADT for biochemical relapse, or those on the "off" phase of a cycle of intermittent ADT will be allowed to enroll on the current study. Though allowing prior ADT for BCR may add heterogeneity with respect to expected disease outcomeswithin the study population, the primary objective of the current study is to investigate whether or not itraconazole has significant biologic activity in this disease setting, as reflected by decline in serum PSA after 12 weeks of therapy. Prior ADT for BCR is not hypothesized to significantly decrease the chance of detecting

PSA decline on itraconazole therapy, though it is acknowledged that prior studies of intermittent ADT have shown that nadir PSA tends to be higher and "off" phase length shorter with successive cycles of intermittent ADT [9]. Furthermore, the role for non-hormonal agents in BCR may eventually fit within the framework of an intermittent ADT strategy, to lengthen the period "off" therapy. As such, including patients with prior ADT for BCR in the current study reflects this potential future application of these agents.

Patients with up to 15 months baseline PSADT can be enrolled onto the current study. Prior studies have shown that pre-treatment PSADT is an independent prognostic factor in the BCR disease setting, and patients with a progressively shorter PSADT have an increasing risk of distant metastases and prostate-cancer specific mortality [38, 39]. Patients with a slow PSA doubling time > 15 months may be more suited to observation alone or local salvage therapies, and as such will be excluded from the current clinical trial.

The minimum PSA required for study entry varies depending on the modality of prior treatment, in keeping with guidelines set forth by the PSA Working Group [36]. In patients with prior radiation therapy (external beam or brachytherapy), the minimum PSA required for study entry is nadir PSA after RT + 2.0 ng/mL, consistent with ASTRO guidelines to define biochemical recurrence [40]. For patients with prior radical prostatectomy, definition of BCR varies by institution, but in general is usually defined as a PSA > 0.4 using a sensitive assay. A minimum PSA of 1.0 ng/mL is chosen for this study to allow for a more accurate determination of baseline

PSADT. For patients with prior ADT for biochemically relapsed disease, as outlined in section 1 of the protocol, there is no standard and commonly accepted definition of PSA progression. In prior clinical trials of intermittent ADT, widely varying PSA thresholds have been used as a "trigger" to re-initiate therapy, ranging from 2-20 ng/mL in absolute value or 25-100% of baseline or nadir PSA. The minimum PSA after prior ADT for BCR utilized in the current study (4.0 ng/mL or > 2 ng/mL above nadir PSA on prior ADT, whichever is higher) is acknowledged to be arbitrary but reflects current clinical practice and prior clinical trials of intermittent ADT, in which the second and subsequent cycles of ADT are often initiated upon reaching a pre-specified absolute PSA level that ranges from 2-20 ng/mL.

Patients with a history of prior androgen deprivation therapy will be required to have a stable serum testosterone level, as defined by the absence of an increase of more than 50 ng/dLbetween consecutive measurementsusing thetwo most recent measurements prior to the initiation of protocol therapy. A rising serum testosterone level may drive the rise in PSA during the period of testosterone recovery, which would then confound efforts to interpret pre-treatment vs. on-treatment changes in PSA doubling time and PSA kinetics, one of the secondary endpoints of the current study. Without attempting to exclude patients in the testosterone recovery phase, a lengthening of the PSA doubling time on therapy may be reflective of a plateau in testosterone recovery rather than a biologic effect of the therapeutic agent being tested.

5.2 Rationale for the Study Design and Dose Selection of Itraconazole

5.2.1 Rationale for the Study Design

The current study is a single arm, phase II trial of itraconazole in patients with biochemically relapsed disease. The primary aim of the study is to assess biological activity of itraconazole at dose of 300 mg PO BID as evidenced by decline in serum PSA \geq 50% from baseline after 12 weeks of protocol therapy. Estimates of historical control PSA response proportions can be fairly accurately estimated based upon the numerous prior studies of non-castrating agents in biochemically relapsed prostate cancer, including the recently published trial of the superoxide dismutase inhibitor ATN-224 [10-16]. In these studies, the biologic activity was modest, with the proportion of patients achieving > 50% decline in serum PSA on therapy usually 5% or less. Preliminary evidence demonstrating substantial modulation of serum PSA with itraconazole, along with acceptable toxicity and minimal impact on the adrenal hormone synthetic pathway, would potentially demonstrate that itraconazole is a viable non-castrating treatment alternative for patients with biochemical relapse and may additionally form the basis for further study of itraconazole in a larger placebo-controlled, randomized phase II/III trial, with adequate statistical power to detect a difference in clinically relevant efficacy endpoints such as time to first metastasis.

Interim analyses with pre-specified stopping rules for safety andlack of efficacy will be carried out after 10 patients have been treated for a minimum of 8 weeks and 30 patients for a minimum of 12 weeks, respectively (see Section 10). Study accrual will continue during the two

plannedinterim analyses, which we feel is acceptable due to the previously well-documented safety profile of itraconazole, continuous safety data monitoring, the relatively asymptomatic nature of the biochemically relapsed non-castrate patient population, and the previously utilized single stage study designs of other non-castrating therapies in the biochemically relapse disease setting.

5.2.2 Rationale for Dose Selection of Itraconazole

Itraconazole is FDA-approved at doses ranging from 100 mg/day to 300 mg PO BID for chronic treatment of invasive fungal infections. High-dose itraconazole (300 mg PO BID) has demonstrated acceptable safety and tolerability in immunosuppressed patients with chronic fungal infections, as well as in a prior phase II trial in patients with CRPC [19], and thus has acceptable prior safety data to justify dosing at 300 mg PO BID in the current study. The protocol contains pre-specified dose reductions for anticipated toxicities (see Section 8) and a stopping rule for safety after the first 10 patients have been treated for a minimum of 8 weeks (see Section 10).

From an efficacy and pharmacodynamic standpoint, the optimal dose of itraconazole in prostate cancer is not yet well-characterized. However, based on the prior randomized phase II study of low- and high-dose itraconazole (200 mg/day and 300 mg PO BID respectively) in metastatic castrate resistant prostate cancer, low-dose itraconazole appeared to have only minimal biologic activity and down-regulated *GLI1* expression in only one third of patients (see Section 1). In contrast, the high-dose study arm demonstrated significant biologic activity and down-regulated *GLI1* expression in approximately two-thirds of patients. Thus, the dose of 300 mg PO BID will be chosen for further study in the current trial.

